To explore potential associations between foods and beverages and hip fracture incidence, food and beverage intake variables in grams per day will be calculated by multiplying servings per day intake variables by standard portion weights, and summing relevant FFQ items. Food and beverage intake variables (grams/day) will be used to explore the effects of increment increases in intake on hip fracture risk, and to categorise participants into non-consumers (if > 1000 participants in this category) and levels of intake for all exposure variables, ensuring equal distribution of the population size among categories where possible. For intakes of milk, tea, coffee, and tea and coffee combined, increment increases and categories of intake will be defined by glasses and cups per day using standard sizes with the lowest exposure category as the reference group. For fruits, vegetables, and fruits and vegetables combined, categories will be defined to compare intakes below and above the

recommended five-a-day (400 g/day) intake, which will be used as the reference category. All other food and beverage exposures will be split into thirds or quarters.

Nutrient variables will be derived by multiplying food and beverage intakes (g/day) by nutrient concentrations in each food or beverage item using McCance and Widdowson’s Food Composition database (5th edition) [2].

4. Outcomes

Participants will be followed up via record linkage to the NHS Hospital Episode Statistics up to 31 March 2019. The primary outcome will be hip fracture incidence (International Classification of Diseases, ICD-9 code 820, and ICD-10 codes S72-S72.2). Hip fracture cases will also be identified by hip replacements (ICD-10 code Z96.64). The timeframe will be person years until hip fracture incidence (or until end of study period or death in those without a hip fracture), calculated as age at time of event (or non-event) minus age at study entry.

5. Sample size

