The minimum detectable hazard ratio for the potential association between each primary exposure and hip fracture was estimated assuming a sample size of 26,300 (after applying exclusion criteria), an overall probability of hip fracture incidence of 3%, $p < 0.05$, and 80% power. For the dietary group analysis, a theoretical standard deviation of the exposure was calculated based on the percentage of participants in each category (Table 2). The minimum detectable effect of other primary exposures was calculated per standard portion size increase in intake using standard deviations of each exposure from the data in hand. Standard portion sizes were estimated from the Foods Standards Agency and previous UKWCS analyses [3, 4]. A standard portion size for total animal products was calculated by averaging standard servings of meat, fish, eggs, and dairy products.

Table 2: Minimal detectable hazard ratios for associations between primary exposures and hip fracture risk.

Exposure	SD	Minimum detectable HR
Dietary group (vegetarians vs non-vegetarians)	0.36	1.32
Fruit and vegetables (per 80 g increase)	300 g	0.98
Fruits (per 80 g increase)	227 g	0.97
Vegetables (per 80 g increase)	139 g	0.95
Total animal products (per 120 g increase)	248 g	0.95
Total meat (per 150 g increase)	81.2 g	0.84
Total fish (per 140 g increase)	28.3 g	0.61
Eggs (per 88 g increase)	18.6 g	0.63
Total dairy (per 105 g increase)	214 g	0.95

Tea and coffee (per cup increase)	2.17 cups	0.96
Tea (per cup increase)	2.01 cups	0.95
Coffee (per cup increase)	1.65 cups	1.06
Protein (per 25 g increase)	26.3 g	0.91
Calcium (per 300 mg increase)	365 mg	0.91
Vitamin D (per μg increase)	1.67 μg	0.94

1 cup of tea or coffee = 260 ml. SD = Standard deviation. HR = Hazard ratio. The SD for dietary group is theoretical and has arbitrary units.

6. Descriptive statistics

Baseline socio-demographic, anthropometric, diet, and lifestyle characteristics of the cohort were collected via questionnaire at baseline, and will be summarised (e.g. presenting their means and standard deviations) by: 1) dietary group (both for data-derived and self-identified dietary group); 2) total fruit and vegetable consumption; 3) total animal product consumption; 4) total tea and coffee consumption, and 5) protein, calcium, and vitamin D intakes, to report any differences in covariates (including co-exposures) between groups at baseline.

7. Statistical modelling

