7.1 Main analyses

We will fit Cox proportional hazard regression models to estimate the hazard ratios (HR) and 95% confidence intervals (95% CI) for associations between 1) the dietary groups and hip fracture incidence, with regular meat-eaters as the reference group; and 2) between intake of: fruits, vegetables, fruits and vegetables combined, total animal products, meat, fish, dairy, eggs, tea, coffee, tea and coffee combined, total protein, calcium, and vitamin D and hip fracture incidence. Each primary food, beverage, and nutrient exposure variable will be modelled as both categorical and continuous so that models can be fit comparing the risk of hip fracture between categories of intakes (where the target estimand is the relative causal effect of the exposure on hip fracture risk) and per increment increase in exposure intake (where the target estimand is the total causal effect of the exposure on hip fracture risk). We will also assess HR's for hip fracture as a function of primary exposure intake (non-linear dose-response) via restricted cubic splines for intake of: fruits, vegetables, fruits and vegetables combined, tea, coffee, and tea and coffee combined, since previous studies have shown non-linear relationships between each of these variables and hip fracture risk [5, 6]. Proportional hazards assumptions will be assessed based on Schoenfeld residuals.

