To estimate the population impact of diet on hip fracture incidence, we will determine the absolute risk difference for hip fracture between dietary groups and categories of exposure intakes, respectively. Predicted incidences and absolute risk differences will be calculated per 1000 person years and per 1000 people over 10 years using hazard ratios and 95% confidence intervals expressed as floating absolute risks [10].

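### The 10-year risks per 1000 people come from hazard ratios with death censored, and the SAP names no method that counts death as a competing event

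*SAP*

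**What the plan says.** SAP section 4 (Outcomes) follows women through "record linkage to the NHS Hospital Episode Statistics up to 31 March 2019". Person-years run to hip fracture, "or until end of study period or death in those without a hip fracture". A woman who dies without a fracture is therefore a non-event, censored at death.

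Section 7.1 fits ordinary Cox models to that time scale.

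The last paragraph of section 7.1.1 gives the purpose of the absolute figures: "To estimate the population impact of diet on hip fracture incidence, we will determine the absolute risk difference for hip fracture". On how they are reported it says: "Predicted incidences and absolute risk differences will be calculated per 1000 person years and per 1000 people over 10 years". They are to be derived from the hazard ratios and their intervals, expressed as floating absolute risks, with a literature reference. The paragraph gives no formula, no baseline risk and no rule for deaths within the ten years.

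Neither the main analyses nor the sensitivity analyses in section 7.3 mention a competing event, a cumulative incidence function or a model for death.

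**The concern.** The two scales in section 7.1.1 treat death differently. A rate per 1000 person-years is sound with deaths censored, because a woman who dies leaves the denominator. A risk per 1000 people over 10 years keeps all 1000 women in the denominator, so it depends on how many die before they could fracture. Converting a death-censored hazard directly gives the risk that would apply if nobody died of anything else. That is a legitimate hypothetical quantity, but it is not the number of fractures to expect among 1000 women, which is how a statement of population impact is read.

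Two things are at stake. Each group's 10-year risk would be too high. The difference between groups would also carry an error that depends on mortality in each dietary group, which the SAP does not plan to examine.

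**Working it through.** **The plan's own figure.** The SAP states no 10-year risk, so the only figure to reproduce is the dietary-group hazard ratio in Table 2, used below as the example effect. Inputs from section 5: 26,300 women, 3% with fracture, SD 0.36, 80% power. Section 7.3 gives a two-sided 0.05 level.

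- Events: 0.03 × 26,300 = 789.
- Minimum detectable HR = exp[(1.960 + 0.842) / (√789 × 0.36)] = 1.319, against 1.32 stated. It reproduces.

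**Assumed inputs.** The SAP gives no fracture rate, follow-up length or mortality.

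- Fracture rate h in the reference group: 1.5 per 1000 person-years. Spreading 3% over 20 years gives −ln(0.97)/20 = 1.52 per 1000; over 15 to 25 years it gives 2.0 to 1.2.
- Death rate m: 5, 10, 20 and 30 per 1000 person-years.
- Constant hazards over 10 years.

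**Formulas.**

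- Deaths censored, converted directly: 1 − exp(−10h).
- Death competing: h/(h + m) × [1 − exp(−10(h + m))].

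**Deaths censored.** Reference: 1 − exp(−0.015) = 14.9 per 1000. Exposed, h = 0.0015 × 1.32 = 0.00198: 19.6 per 1000. Difference: 4.72 per 1000.

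**Death competing, equal mortality in both groups** (per 1000 over 10 years):

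| Death rate per 1000 person-years | Reference risk | Exposed risk | Difference | Excess in reference risk | Excess in difference |
|---|---|---|---|---|---|
| 5 | 14.5 | 19.1 | 4.60 | 2.5% | 2.5% |
| 10 | 14.2 | 18.7 | 4.49 | 5.1% | 5.1% |
| 20 | 13.5 | 17.8 | 4.28 | 10.3% | 10.3% |
| 30 | 12.9 | 16.9 | 4.08 | 15.7% | 15.6% |

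The excess columns compare the censored figures (14.9 and 4.72) with the competing-event figures. The relative excess hardly depends on h: with h between 1.2 and 2.0 per 1000 the reference-risk column is the same to one decimal.

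**Unequal mortality.** Reference death rate 10 per 1000 person-years; the mortality ratio is exposed to reference:

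| Mortality ratio | True difference | Censored figure of 4.72 is |
|---|---|---|
| 0.7 | 4.77 | 1.1% too low |
| 0.8 | 4.67 | 0.9% too high |
| 0.9 | 4.58 | 2.9% too high |
| 1.2 | 4.31 | 9.5% too high |

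To leading order, death removes about h × m × 10²/2 from each group's risk. The error in the difference is therefore proportional to HR × mortality ratio − 1. It changes sign near a mortality ratio of 1/1.32 = 0.76; the exact break-even at this death rate is 0.754.

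**The case against.** **The conversion is inferred.** Section 7.1.1 names hazard ratios and floating absolute risks but gives no formula, and the cited source is not at hand. If the hazard ratios were applied to an observed 10-year proportion with every recruit in the denominator, deaths would already be partly reflected. This stands, so the excess is conditional on direct conversion. It does not remove the point: nothing in the SAP says that deaths are counted, and a computation left open needs to be fixed.

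**The size is small and assumed.** With 789 events and SD 0.36, the standard error of log HR is 1/(√789 × 0.36) = 0.099. An HR of 1.32 then has a 95% interval of about 1.09 to 1.60, which at the assumed baseline is a risk difference of about 1.3 to 8.9 per 1000. A shift of 0.1 to 0.6 per 1000 sits well inside that and would be unlikely to change a conclusion. This stands and keeps the point minor. It remains a systematic error, which more data would not reduce.

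**Stronger readings that the SAP does not support.** A reader might infer that the plan necessarily overstates population impact. The impact measure is the risk difference, and its upward bias is certain only under equal mortality; the SAP gives no mortality by dietary group. A reader might also infer that the planned results in women over 60 are badly distorted. Section 7.2.1 stratifies the models by age to look for effect modification. Section 7.1.1 promises absolute risks by dietary group and intake category, and does not promise 10-year risks by age.

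**Conclusion.** The point holds in a limited form. The 10-year figures per 1000 people rest on hazard ratios with death censored, they are offered as population impact, and no method is named that treats death as a competing event.

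Under direct conversion, any mortality above zero makes each group's 10-year risk too high as a real-population risk. The sizes in the working rest on constant hazards and on assumed fracture and death rates. The proportional error in the risk difference matches that in the risks only when the groups have equal mortality. With unequal mortality it can shrink, grow or change sign.

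The Cox hazard ratios and the rates per 1000 person-years need no change on this account. This is a worthwhile, inexpensive improvement and does not threaten the main analysis.

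**What to change.** In the absolute-risk paragraph of section 7.1.1:

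- State how the 10-year risks are computed, including the baseline to which the hazard ratios are applied.
- Compute the 10-year risks and risk differences as cumulative incidence with death as a competing event. Combine the fracture Cox model with a Cox model for death without fracture, and take bootstrap intervals.
- Give the death model its own adjustment set. The graphs planned in section 7.1.1 are built for hip fracture and need not identify the confounders of diet and death.
- Keep the hazard ratios and the rates per 1000 person-years as planned.

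Minimum alternative: label the 10-year figures as risks in the hypothetical absence of death and do not present them as population impact.

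Cost: one extra model with its covariate set for each exposure, some code and bootstrap time, and slightly smaller reported absolute risks. Death dates are already needed to end follow-up under section 4, so no new data are required. The labelling alternative costs a sentence.

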7.2 Subgroup analyses

7.2.1 Dietary group

We will stratify all models by age (<60, > 60), BMI (<23.5, >23.5), SES (routine/manual, intermediate, professional/managerial), education (\geq A level, \leq O level), smoking status (current, former/never), alcohol consumption (< 1/week, \geq 1/week), menopausal status (pre, post), physical activity levels (inactive/low, moderate/high), and use of dietary supplements (yes/no) to determine their roles as potential effect modifiers. Effect modifiers will be defined as any covariate that meets the criteria for a confounder (previously defined) and could plausibly modify the association at varying levels of that covariate. Potential effect modifiers will also be added to all models as interaction terms. Models stratified by calcium, vitamin D, and vitamin B12 supplement use will be presented in those with phase 2 questionnaire data only, since this was not collected at baseline.

7.2.2 Foods, beverages and nutrients

We will fit additional Cox models for types of meat (unprocessed red, all processed, and unprocessed poultry), fish (oily and non-oily), dairy (milk, yoghurt, cheese, cream, and dairy desserts), and coffee (caffeinated and decaffeinated) intakes, treating each exposure intake as both categorical and continuous.

We will stratify models for combined fruits and vegetables consumption, combined tea and coffee consumption, and protein, calcium, and vitamin D intakes by age, BMI, menopausal status, and use of dietary supplements to determine their roles as potential effect modifiers, and will add these variables to fully adjusted models as interaction terms. The same cut-off points will be used as in the vegetarian diets analysis (section 3.2). The effect of protein intake on hip fracture will be further stratified by physical activity and calcium intake. We will also present models for all dietary exposures stratified by calcium and vitamin D supplement use in those with phase 2 questionnaire data only.

7.3 Sensitivity analyses

For the dietary group analysis, we will present models with vegans and vegetarians separated. We will also compare risk estimates between self-identified and data-derived dietary groups. For all analyses, we will explore the potential mediating effect of covariates identified in DAG models as being associated with hip fracture incidence and plausibly caused by the exposure by adding each of these covariates to adjusted models independently. Models will be presented with and without adjustment for BMI. To reduce risk of bias due to changes in exposure over time, phase two dietary data (collected four years after baseline) will be compared with baseline dietary data. In cases of substantial exposure change over time (e.g., > 10% of participants changing their dietary group or primary exposure categories), models will be repeated using phase two data if there is sufficient power.

Additional sensitivity analyses will involve excluding cases occurring in the first five years of follow-up (to check for reverse causality), and excluding participants on long-term treatment for illnesses. All analyses will be performed using Stata. Two-sided p values < 0.05 will be considered statistically significant. We acknowledge that the large number of planned exposure-outcome association tests increases the risk of a type-2 error. However, the alpha value will not be restricted below $p < 0.05$ since secondary analyses (including most nutrient-hip fracture associations) will be exploratory, with only the primary analyses considered hypothesis-testing. All analyses performed and effect sizes computed will be presented in resulting manuscripts to avoid bias in selection of the reported result.

8. Missing data

Participants with missing data for an FFQ item will be considered non-consumers. Participants will be excluded from each specific analysis if they have missing data for any other variable required in that analysis. Techniques to impute missing dietary or covariate data will not be performed.

9. Timescales

Target analysis completion date (excluding manuscript preparations): Jan 2021.

10. References

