3.1 Primary and secondary exposures

The primary exposures of interest are data-derived dietary group (regular meat-eater, occasional meat-eater, pescatarian, vegetarian, or vegan – see Table 1 for definitions) and dietary intake of foods, beverages, and nutrients, including: 1) fruits and vegetables; 2) animal products including meat, fish, eggs and dairy products; 3) tea and coffee, and 4) nutrients associated with hip fracture in previously published studies (protein, calcium, and vitamin D).

Secondary exposures of interest include self-identified dietary group (meat-eater, pescatarian, vegetarian, or vegan), types of meat (unprocessed red, all processed meat, and unprocessed poultry) and dairy products (milk, yoghurt, cheese, cream, and dairy desserts), caffeinated and decaffeinated coffee, and nutrients with a plausible association with hip fracture (such as phosphorus intake). All relevant exposures and their derivation are listed in Supplementary Table 1.

Table 1: Data-derived dietary group categories and definitions.

Dietary group	Definition
Regular meat-eater	Total meat intake ≥ 0.8 servings/day

Occasional meat-eater	Total meat intake < 0.8 servings/day & > 0.02 servings/day
Pescatarian	Total meat intake ≤ 0.02 servings/day & total fish intake > 0.02 servings/day
Vegetarian	Total meat and fish intakes ≤ 0.02 servings/day, intake of any dairy products or eggs > 0.02 servings/day
Vegan	Total meat, total fish, dairy products, and eggs intake ≤ 0.02 servings/day

Participants with consumption frequencies ≤ 0.02 servings/day (less than once a month) will be considered non-consumers.

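### The comparison of self-identified with data-derived dietary groups (SAP 7.3) fixes no common reference group, so the vegetarian/vegan hazard ratios can differ without any misclassification

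*SAP*

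**What the plan says.** Four places in the SAP bear on this.

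- **Section 3.1, primary exposure:** "data-derived dietary group (regular meat-eater, occasional meat-eater, pescatarian, vegetarian, or vegan". Table 1 separates the two meat-eating groups by intake: regular is "Total meat intake ≥ 0.8 servings/day" and occasional is "Total meat intake < 0.8 servings/day & > 0.02 servings/day".
- **Section 3.1, secondary exposure:** "self-identified dietary group (meat-eater, pescatarian, vegetarian, or vegan". There is one meat-eater level and no frequency split. Section 3.2 describes the underlying questionnaire item as offering meat-eater, vegetarian or vegan; it names neither a split of meat-eaters nor a pescatarian option.
- **Section 7.1:** Cox models are fitted for "the dietary groups and hip fracture incidence, with regular meat-eaters as the reference group".
- **Section 7.3:** "We will also compare risk estimates between self-identified and data-derived dietary groups".

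The SAP does not state a reference group for the self-identified model, and does not say that the data-derived meat-eating groups will be combined for the comparison.

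**The concern.** A comparison of two classifications is informative about classification only if that is all that changes. Here two things change together: who is called vegetarian or vegan, and whom they are compared with. The data-derived estimate is relative to regular meat-eaters. That level does not exist in the self-identified variable, whose natural reference is everyone who calls herself a meat-eater.

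A gap between the two hazard ratios could then be taken as self-report error or as fragility of the dietary-group result, when it comes from the comparator. In the other direction, a shift in the reference could offset a real classification effect and make the two results look consistent. The dietary-group analysis separates regular from occasional meat-eaters, so equal risk in those two groups should not be taken for granted.

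This is distinct from whether a self-identified pescatarian level exists. It concerns the vegetarian/vegan hazard ratio, which both classifications can produce.

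**Working it through.** **1. The plan's own figure.** Inputs from SAP section 5: 26,300 women, 3% hip fracture probability, 80% power, p < 0.05 (two-sided by section 7.3), and SD 0.36 for dietary group.

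- Events: 26,300 × 0.03 = 789.
- Minimum detectable HR: exp[(1.960 + 0.842) / (0.36 × √789)] = 1.319. Table 2 gives 1.32, so the figure reproduces.

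Table 2 labels this contrast as vegetarians versus non-vegetarians. It is a detectable size, not an expected effect, and not a contrast with regular meat-eaters. Below, 1.32 is used only as an assumed size for the vegetarian versus regular meat-eater HR.

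**2. The two references side by side.**

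| | Data-derived | Self-identified |
|---|---|---|
| Meat-eating levels | Regular (≥ 0.8/day); occasional (> 0.02 and < 0.8/day) | One: meat-eater |
| Reference | Regular only (stated, 7.1) | All meat-eaters (inferred) |

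**3. Size of the shift with perfect self-report.** Let *s* be the share of meat-eaters who are occasional and *h* the occasional versus regular HR. Neither is in the SAP; both are assumed. The hazard of the pooled reference relative to regular meat-eaters is approximately (1 − *s*) + *s* × *h*, so

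HR against all meat-eaters ≈ 1.32 / [(1 − *s*) + *s* × *h*].

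| *h* | *s* = 30% | *s* = 50% | *s* = 60% |
|---|---|---|---|
| 0.90 | 1.32/0.970 = 1.36 | 1.32/0.950 = 1.39 | 1.32/0.940 = 1.40 |
| 1.00 | 1.32 | 1.32 | 1.32 |
| 1.05 | 1.32/1.015 = 1.30 | 1.32/1.025 = 1.29 | 1.32/1.030 = 1.28 |
| 1.15 | 1.32/1.045 = 1.26 | 1.32/1.075 = 1.23 | 1.32/1.090 = 1.21 |

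For *h* between 1.05 and 1.15 the log HR shrinks by 5% (1 − ln 1.3005 / ln 1.32) to 31% (1 − ln 1.211 / ln 1.32). For *h* = 0.9 it grows instead. For *h* = 1 nothing moves.

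**4. With a common reference.** If both models use all meat-eaters, the divisor applies to both and the part of the gap due to the regular/occasional split is zero.

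**The case against.** The case against giving this much weight is substantial.

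- **The pooled reference is inferred.** The SAP names no reference for the self-identified model and does not say how the estimates will be compared. This stands, but no narrower meat-eating reference can be formed from that variable alone, and nothing in the plan harmonises the two.
- **Existence and direction of the shift are unknown.** Both depend on an occasional-group HR that the SAP does not give. This stands too, and is why the table spans values below, at and above 1.
- **The plan already shows much of what is needed.** The main model will report the occasional versus regular HR, and section 7.3 promises that all effect sizes will be presented. A careful reader could judge whether the reference matters, but would have to work out the like-for-like figure.
- **It is peripheral.** Self-identified group is a secondary exposure, secondary analyses are declared exploratory, and no decision rule rests on the comparison. This stands and limits the weight of the point.
- **Merging the meat-eaters is not enough by itself.** Without a pescatarian option in the questionnaire item, women who eat fish but not meat may sit in the meat-eater or vegetarian level on one side and in their own level on the other. This stands, and the fix has to cover it.

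A reader might also infer that the reference alone will make one result significant and the other not. The documents do not support that as a general statement. The broader reference has more events, which can offset a smaller HR. As a rough check, take 789 events split by group share, 15.3% vegetarians (from SD 0.36) and an assumed 10% pescatarians, leaving 74.7% meat-eaters, with power = Φ(|ln HR| × √[d·p(1 − p)] − 1.96). Here *d* is the events in the two groups compared and *p* the vegetarian share of them. Power for the data-derived versus the self-identified contrast is then about 73% versus 54% at *s* = 50%, *h* = 1.149; 77% versus 75% at *s* = 30%, *h* = 1.05; and 70% versus 70% at *s* = 60%, *h* = 1.05. The conclusion depends wholly on assumed inputs.

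**Conclusion.** The point holds as a limited one. As written, the section 7.3 comparison mixes a change of comparator with a change of classification, and the vegetarian/vegan hazard ratios can differ with no misclassification whenever occasional and regular meat-eaters differ in risk.

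In the illustration the shift takes an HR of 1.32 to somewhere between about 1.21 and 1.40, depending on the assumed share (30% to 60%) and occasional HR (0.9 to 1.15), and is zero at equal risk. These are assumptions, not figures from the SAP. The conclusion also rests on the inference that the self-identified model will use all meat-eaters as its reference.

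Two stronger readings should be avoided. Table 2's 1.32 does not describe vegetarians against regular meat-eaters, so it cannot be cited as the plan's effect for that contrast. And no fixed loss of power or change of significance can be claimed. The main dietary-group analysis, its reference group and the sample size are unaffected. The matter is minor, and worth correcting because it is so cheap.

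**What to change.** Add to section 7.3 that, for this comparison only:

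- the data-derived model will be refitted with regular and occasional meat-eaters combined (total meat above 0.02 servings/day) as the reference, and the self-identified model will use its meat-eater level;
- both models will be fitted on the same women with the same adjustment set;
- pescatarians will be handled identically in both classifications: as a separate level if one can be derived for the self-identified variable, otherwise assigned the same way in both;
- the refitted vegetarian/vegan HR, not the one from the main model, is what will be set against the self-identified HR.

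The main data-derived analysis keeps regular meat-eaters as its reference. The cost is a short addition to the SAP, one extra model on existing data and one more row in the sensitivity table.
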